If more than one household resident is interested and eligible in the study, the person with the most recent birthday will be enrolled. One participant per household is eligible. The CC team will conduct an informed consent with all participants. The CC team will then administer a demographic and baseline survey and directly enter data into REDCap. If the resident is interested in the study but is not available or able to complete the baseline survey at the time of the first encounter, CC team will conduct the Informed Consent Process (resident will sign the Informed Consent Form) and then identify a time to reschedule complete the baseline survey. If necessary, the CC team can schedule to meet with the resident virtually to complete the baseline survey.

Completion of the baseline survey indicates resident is fully enrolled in the study and is to be considered the official date of enrollment.

If there are one or more children ages 3-17 living in the household, the child or children's primary caregiver will be given the option of completing an additional follow-up survey regarding their child's health and wellbeing. One participant per household is eligible to complete the children's health and well-being survey for up to three children residing in the household. If more than three children ages 3-17 reside in the household, the enrolled caregiver will be asked to complete the survey for the three children with the most recent birthdays. We will enroll adult caregivers of approximately 480 children ages 3-17. To meet this goal, approximately up to 240 additional caregivers will be enrolled. Towards this end, after enrollment of adult subjects is complete within a microcluster, CC teams will continue to enroll caregivers from homes within a microcluster with which contact has not already been made. Enrollment will end when either enough caregivers are enrolled for up to 10 children per microcluster or two weeks after adult enrollment closes within the microcluster.

Subject compensation

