Several Community Coordinator (CC) teams will be recruiting participants. A given team of two will remain in a microcluster until at least 8participants are fully enrolled in that microcluster. They will then move to the next microcluster on the randomly generated list. Multiple microclusters will be undergoing enrollment simultaneously. The CC team will be blinded to what arm of the trial the microcluster is in until all participants are enrolled. Participants will also be blinded until after everyone in that cluster is enrolled.

When starting recruitment in a new microcluster, the CC team will first place door knockers on all homes within the microcluster boundaries to alert neighbors to the presence of the study team in the neighborhood. They will then begin door-to-door recruitment at a pre-determined house that is closest to the geographic center of the study microcluster. They will follow a pre-determined route throughout the neighborhood that includes walking up one side of the street and back down the other side of the street before moving on to an adjacent block, and the next adjacent block, etc. The block order will be pre-determined by the data analyst performing randomization to where blocks will be ordered as closet to concentrically in a clockwise manner from the first block.

For a given house, a potential participant will be screened by the CC team to determine eligibility:

Key Inclusion Criteria:

- At least 18 years of age
- Have the ability to communicate via text messaging

- Individuals comfortable communicating in English
- A permanent resident of the home where they are to be enrolled
- Have knowledge of their household finances

Key Exclusion Criteria:

- Individuals who plan to move out of the study microcluster within 6 months
- Individuals who are unable to fully consent and participate based on CC team assessment

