IGNITE Kids referrals. To support enrollment efforts for the IGNITE Kids sub study, participants may also be asked if they know of and are willing to connect the study team to any families in their neighborhood with children ages 3-17. Participants will be compensated \$10 for successful referrals. Referrals for IGNITE Kids will count towards the 2-referral limit described above.

Tree referrals. To support efforts in planting at least 10 trees in each intervention microcluster, participants will be invited to refer neighbors who may be willing to receive free trees through the study. Referrals may be accepted at the time of enrollment and/or during subsequent home visit(s). Participants will be compensated \$10 for successful referrals. Participants can make and be paid for an unlimited number of tree referrals or for the amount needed until tree planting goals have been met in their particular microluster.

Intervention

Place-Based Interventions

Our suite of place-based interventions consists of four separate interventions which will all be performed simultaneously in all of the intervention microclusters. The four interventions are: vacant lot greening, tree planting, weekly trash pickup, and abandoned house remediation. The first three will be performed through the Pennsylvania Horticultural Society (PHS), while the last will be performed through the City of Philadelphia.

After microclusters have been selected and randomized to the intervention arm (n=30), we will conduct an inventory of the locations of existing vacant lots, abandoned houses, and tree canopy. All place-based interventions will start in April 2023. See below for protocol for each intervention including the intervention timeframe for each.

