Tree planting. We will plant a total of 300 trees in the intervention microclusters during this study, or roughly 10 trees per cluster. Trees will be planted between September and October 2023, with monthly watering occurring between planting and August 2024 during the growing season. We anticipate that some clusters may receive less than 10 trees and other clusters will receive more than 10 trees based on availability of planting opportunities. Trees will be planted and maintained through PHS. In Philadelphia, permission is needed from the owner of a property to plant a tree. After all participants in an intervention microcluster are enrolled and the microcluster randomization is revealed to the community coordinator team, all participants who indicated they were interested in a tree will have a tree planted in front of their residence based on the following criteria: (a) there is an open space for a tree, (b) there are no physical barriers to tree planting (eg fire hydrant), and (c) the owner of the property lives in the home and is able to give permission to plant a tree. If the participants rents the property, we will determine if they would like to seek permission from the landlord. After we determine which study participants are eligible for a tree, we will then canvas the neighbourhood microcluster to find other residents, businesses, places of worship, etc in the cluster who are not participants in the study who want a tree planted, for a total of 12-15 potential tree planting opportunities. We know that some tree planting sites will

ultimately not be eligible for planting which is why we will initially select 12-15 sites with the aim of planting 10 trees per cluster. This list will then be sent to the PHS who will work with the City of Philadelphia to determine which physical locations are eligible for a tree. For example, sometimes there are water lines too close to the side-walk surface that make a location ineligible.

Trash cleanup. We will provide weekly trash cleanup in all public spaces in the blocks included in our intervention clusters between April 2023 and August 2024. Public space includes on streets and sidewalks, but not into private front yard space. Although the city performs weekly trash pickup, this is limited to trash that is in garbage cans, leaving neighborhoods with a significant trash burden that does not fall under the purview of regular sanitation. Trash cleanup will occur through PHS.

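### Paid tree referrals, which serve only intervention microclusters, may be taken at a person's enrolment without saying in which arms; if invited only in intervention clusters, they would break the recruitment blind

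*Combined protocol and SAP*

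**What the plan says.** Two blinding rules stand in both Section 6 (Subject recruitment) and Section 8.2 (Enrollment). For coordinators: "The CC team will be blinded to what arm of the trial the microcluster is in until all participants are enrolled". For residents: "Participants will also be blinded until after everyone in that cluster is enrolled".

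Section 6 also fixes what enrolment means for one person: "Completion of the baseline survey indicates resident is fully enrolled in the study and is to be considered the official date of enrollment". It is an individual date, not the closing of the cluster.

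The tree-referral paragraph of Section 8.2 (under Respondent Driven Sampling) gives the purpose: "To support efforts in planting at least 10 trees in each intervention microcluster, participants will be invited to refer neighbors". On timing it says: "Referrals may be accepted at the time of enrollment and/or during subsequent home visit(s". A successful referral earns $10. On volume: "Participants can make and be paid for an unlimited number of tree referrals", or as many as are needed "until tree planting goals have been met in their particular microluster".

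The Tree planting paragraph of Section 8.2 puts all 300 trees in intervention microclusters. It allots trees to interested participants, and canvasses non-participants for further sites, after the cluster is fully enrolled and "the microcluster randomization is revealed to the community coordinator team".

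**The concern.** Clusters are randomised first and residents are recruited door to door afterwards. In that design, keeping recruiters and residents unaware of the arm is a key protection against the two arms enrolling different kinds of people. A task that exists for one arm only, and that may be carried out at the enrolment visit, sits badly with that blind.

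At stake is who enters the trial. A coordinator who knows the arm could, without intending to, apply the exclusion that rests on the team's own assessment of capacity to consent and take part differently in the two arms. Residents who learn that trees are coming might be more willing to join. Both primary outcomes are self-reported. Adjustment for the baseline outcome and for observed imbalances, as planned in Section 9, cannot remove selection on characteristics that were not measured.

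**Working it through.** The plan gives no figure on this point, so the check sets the passages side by side and then bounds the exposure.

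**1. Does the enrolment visit come before the cluster closes?** Yes, for everyone but the last person enrolled. Section 6 dates enrolment at each person's baseline survey. The tree-referral paragraph contrasts enrolment with later home visits, so it means the individual's enrolment visit. Coordinators stay in a cluster until at least 8 participants (Section 8.2) or 12 (Section 6) are enrolled.

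**2. Which arms are invited?** The purpose and the payment cap both refer to a planting goal, and a goal is stated only for intervention clusters (300 trees / 30 clusters = 10 per cluster). The invitation itself is addressed to participants without naming an arm.

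**3. The possible readings.**
- *Intervention clusters only, at enrolment.* The coordinator must know the arm to make the invitation, and the participant can infer it. This contradicts both blinding rules.
- *Both arms, at enrolment.* The arm is not disclosed. Control participants are asked to put forward neighbours for trees that the plan does not provide there. The payment for a successful referral, and the cap at the cluster's goal, then have no defined meaning, because a control cluster has no goal. A blinded coordinator could not apply that cap.
- *Intervention clusters only, after the reveal.* This fits the blinding rules and the Tree planting sequence. The text permits it through the later home visits but does not require it.

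**4. Ceiling on exposure under the first reading.** Suppose disclosure happens at the first enrolment in a cluster of size n. The share recruited afterwards is (n − 1)/n.
- n = 8: 7/8 = 87.5%. Over 30 intervention clusters, 30 × 7 = 210 of 30 × 8 = 240.
- n = 12: 11/12 = 91.7%. Over 30 intervention clusters, 30 × 11 = 330 of 30 × 12 = 360.

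**5. Caregivers.** Section 6 lets coordinators go on enrolling caregivers, at homes not yet contacted, until there are enough for up to 10 children in the cluster or two weeks have passed after adult enrolment closes (up to about 240 additional caregivers across the trial). A rule tied only to the close of adult enrolment would leave this recruitment exposed.

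**The case against.** The strongest reply is that nothing here requires unblinding. The paragraph names no arm, its timing is permissive, and a coordinator who obeys the blinding rules could not make an arm-selective invitation at the doorstep. The Tree planting text also speaks of participants who had already indicated interest, which suggests that tree interest is recorded before the reveal. Names taken early could simply be held until canvassing. All of this stands. It shows that the passages can be reconciled, not that the plan has reconciled them.

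A second reply is that the blind is not alone. There is a fixed starting house, a set route and block order, a most-recent-birthday rule within the household, simultaneous recruitment in both arms in randomised order, and adjusted analysis. This also stands. These measures limit who is approached and correct for measured imbalance. They do not govern who opens the door, who agrees, or whom the team judges unable to take part.

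A third reply is that asking in both arms does no statistical harm, and that a baseline tree-interest question also raises trees with control participants. This is largely right: what remains under that reading is a matter of communication and payment, not selection bias. An interest question, however, does not ask a control participant to bring in neighbours or attach a payment to doing so.

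A reader might also infer that participants are sent along the recruitment route to advertise trees. The text says only that they refer neighbours. It does not say that they canvass, or that those neighbours are households still to be approached.

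**Conclusion.** The point holds in conditional form. The plan permits an intervention-specific, paid task at individual enrolment visits and does not say in which arms. One reading breaks the blind; the other makes control participants an offer that the plan does not support. The passages need to be reconciled.

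It is tempting to conclude that the arm is disclosed from the first participant in every intervention cluster. The documents do not support that. It would follow only if the invitation were confined to intervention clusters and made at enrolment, and neither is stated as a rule.

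The range of 7 of 8 to 11 of 12 participants per intervention cluster is therefore an upper bound on those recruited after disclosure. It assumes the intervention-only reading and disclosure at the first enrolment. It says nothing about the size or direction of any bias in the outcomes, which the documents give no means to estimate. A correction is still worth making, because it is small and removes a permission that is unsatisfactory whichever arms are invited.

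**What to change.** In the tree-referral paragraph of Section 8.2, strike the part of the timing sentence that allows acceptance at enrolment. State instead that tree referrals are invited and accepted only after the microcluster's enrolment, including additional caregivers, has closed and its arm has been revealed. This matches the sequence already given under Tree planting. Any tree-interest question at baseline should be worded neutrally and asked identically in both arms.

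The edit is one or two sentences. Its cost is that candidate sites are listed somewhat later in each intervention cluster, although Tree planting already schedules canvassing for sites after the reveal. Clusters that close late may be tight against the September to October 2023 planting window, since Section 6 lets recruitment run to March 2024. That tension already exists in the plan's own sequence, but the edit removes early listing as a way to ease it.

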Abandoned house remediation. We will remediate 90 abandoned houses in the intervention clusters during this study, or approximately 3 houses per cluster. Remediation will take place between April and August 2023. Abandoned house remediation follows a standard protocol and includes (1) replacement of plywood boards or missing/broken doors and windows on the front façade of the house with new, standard, exterior, front entryway, wooden doors and standard, double-hung, wooden windows; (2) removal or replacement of deteriorated structures on front building façade; and (3) cleaning and graffiti removal on building façade. A master list of publicly owned abandoned houses in our study intervention clusters will be compiled using publicly available data from the City of Philadelphia. We will not include privately owned abandoned houses in the trial. If there are more than 3 eligible abandoned houses in a cluster, we will randomly sort the list and select the top 3 houses to remediate. Remediation will be conducted through the City of Philadelphia.

Individual and Household-Level Financial Interventions

Participants in the intervention group will be directly connected to three Philadelphia-based community-based partners who specialize in improving access to financial services and public benefits among low-income individuals. The partners and the services provided are:

- Clarifi provides free financial counseling, starting with a detailed intake process that includes elicitation of financial goals and development of an action plan over multiple sessions.
- Benefits Data Trust (BDT) provides free integrated services that screen participants for eligibility for public sector benefit programs (e.g., Medicaid, SNAP, WIC, and nearly 20 other local, state, and national programs) as well as facilitating applications for those benefits.
- Campaign for Working Families (CFW) provides free tax preparation services for families and individuals earning less than \$55,000/year.

In addition to these services, participants living in intervention microclusters will also be eligible to receive a one-time \$400 cash grant, which will be administered by Clarifi. The cash grant will address both potential direct and opportunity costs of working closely with partners (e.g., potential travel costs or lost wages) as well as general financial insecurity the participant and their household may be facing at baseline.

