For this cluster randomized trial, we assume a Type I error rate of 0.05 and a desired power of 0.8 for the primary outcomes. Our study will include 60 microclusters (30 intervention, 30 control) with at least 8 participants in each cluster (n=480 across all clusters). We will have no fewer than 480 and can enroll up to 720. The number of participants enrolled will depend on our dynamic enrollment strategy that we've discussed already. We assume an intraclass correlation (ICC) of 0.05. For our primary outcomes (and all survey-based outcomes), we will fit a marginal model using generalized estimating equations (GEE) to estimate the effect of the intervention relative to control. Under these assumptions, we will be able to detect an intervention effect of 0.33 s.d at 80% power with 30microclusters per arm (60 total) and 8 participants per microcluster.⁹ This is a conservative estimate of power since we will adjust for the baseline value of the outcome and other covariates associated with the outcome. If we are only able to sample from 50 microclusters (25 per arm; n=400 across all clusters), we will be able to detect a moderate effect size of 0.37 s.d. at 80% power. Assuming up to 25% attrition between baseline and endline, we would still be able to detect a treatment effect of 0.31 s.d.

Statistical Analysis

Individual-level primary and secondary outcomes

For all primary and secondary outcomes drawn from our two-wave survey of 720 trial participants, we will assess differences in outcomes between the intervention and comparison groups using Generalized Estimating Equation models (GEE) that account for clustering at the study microcluster level. We will use canonical link functions for all outcomes. All models will adjust for the baseline level of the outcome, all microcluster-level characteristics used in the covariate constrained randomization (see randomization protocol),¹⁰ any individual characteristics found to be imbalanced between the intervention and control groups at baseline.

We will conduct an intention-to-treat analysis: participants that move out of (or across) study clusters, separately engage with community partner services while in the control group, or do not engage with these services while in the treatment group will all be considered exposed to their original treatment assignment.

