Second, we will assess changes in key process measures, namely aggregate information on participation in specific social programs, tax returns and refunds, and credit scores. Per agreement with the community financial organizations partnering on this study, this information would only be available at the aggregate level for the treatment group. However, the degree of engagement in different financial services can help assess which services may have been more important in driving intervention effects. For example, if participants in the treatment group on average received large tax refunds, but did not sign up for new benefit programs, that would implicate the former as a potential mechanism (though without information counterfactual changes in the outcome in the control group, this cannot be proven).

Third, we will assess whether estimated intervention effects were larger among individuals who were most likely to benefit from different program components. For example, individuals who at baseline were not

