accessing major public benefits or who had not filed tax returns prior would be more likely to benefit from financial interventions than those already engaged with these activities. Similarly, individuals living in study clusters with relatively larger numbers of abandoned lots, fewer trees, or more abandoned homes would stand to benefit more from the environmental interventions than those who did not. Formally, we will estimate versions of our main GEE models for the primary outcomes in which we will include interactions between the treatment indicator and binary indicators for individuals participating in fewer than sample median number of public benefit programs; not filing (or had someone file on their behalf) a tax return in the previous year; being below the median of the household financial security scale; living in a microcluster below the median in terms of tree canopy; living in a microcluster that is above the median in terms of the number of abandoned lots; and living in a microcluster that is above the median in terms of the number of houses. Positive and statistically significant coefficients on these interaction terms would provide suggestive evidence that the specific intervention that would address the pre-intervention attribute in question helped drive treatment effects. For example, a positive and significant coefficient on the interaction between treatment and living in a cluster with above the median numbers of abandoned lots would suggest that abandoned lot remediation played a role in driving overall treatment effects. Interpretation of these coefficients requires knowledge of actual exposure to treatments; e.g., it would be more credible to conclude that provision of tax preparation services helped drive health outcomes if large numbers of intervention group participants reported using these services.

Primary Outcomes				
Outcome	Measure	Data Source	Type of Data	Timeframe
Overall Health Index	Composite index using method of Anderson (2008) based on three questions: rating of overall health (5-pt Likert ranging from poor to excellent); rating of how health has changed in last 6_months (better, same, worse); and number of days in the last 30 where physical or mental health precluded engagement in usual activities (self-care, work, recreation); (Oregon HIE)	Survey	Continuous (index)	Baseline, 24 months
Psychological distress	Kessler-6	Survey	Continuous (scale)	Baseline, 24 months
	Secondary Out	comes		

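### No control-arm source is described for abandoned-house counts or partner-service use, which limits one planned interaction and the contingent treatment-on-the-treated analysis

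*Combined protocol and SAP*

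**What the plan says.** **Place-based attributes.** Section 8.2 (Place-Based Interventions) states: "After microclusters have been selected and randomized to the intervention arm (n=30), we will conduct an inventory" of vacant lots, abandoned houses and canopy. Under Abandoned house remediation it adds: "A master list of publicly owned abandoned houses in our study intervention clusters will be compiled", drawing on public City data. Under Randomization, vacancy and tree canopy are among the covariates calculated for every microcluster before allocation.

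Section 9 (Evaluating Mechanisms, third approach) interacts treatment with six baseline attributes. The last is "living in a microcluster that is above the median in terms of the number of houses". The sentences leading up to it argue from the number of abandoned homes.

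**Financial services.** Section 8.2 says the partners' services are open to city residents in general. Section 9 (Statistical Analysis) keeps in their assigned arm those participants who "separately engage with community partner services while in the control group". Section 8.2 describes attendance checks for intervention participants. Of the partners' records on programmes, tax returns and credit scores, Section 9 says that "this information would only be available at the aggregate level for the treatment group".

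The fourth sensitivity analysis would estimate treatment-on-the-treated effects if non-adherence exceeds about 20%. It gives no estimator and no measure of receipt among controls. Controls are sent the partners' contact details when the intervention period ends in August 2024; follow-up surveys run from September 2024 to March 2025.

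**The concern.** An interaction between treatment and a cluster attribute can be estimated only if the attribute is known in both arms. For abandoned houses, the plan describes a source for one arm only and prints a different variable. Followed literally, the model would either use total houses, which does not address the remediation component, or lack the attribute in half the clusters.

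Scaling an intention-to-treat effect by participation needs participation in both arms unless control participation is known to be zero. The plan expects some control use of the same partners but describes no way to measure it. At stake is what the mechanism analysis and the contingent scaled estimate can support. Whether the package as assigned changed the primary outcomes can be answered either way.

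**Working it through.** **1. Which moderators have control-arm values?**

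| Moderator (Section 9) | Described source | Control arm? |
|---|---|---|
| Number of public benefit programmes | Baseline survey, Table 1 | Yes |
| Tax filing | Baseline survey, Table 1 | Yes |
| Household financial security | Baseline survey, Table 1 | Yes |
| Tree canopy | Randomization covariate, all 60 clusters | Yes |
| Abandoned lots | Vacancy covariate for all 60, or post-allocation inventory, or horticultural society list overlaid on cluster boundaries (arm not named) | Unclear |
| Houses | Inventory and City list, intervention clusters | None described |

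Four are covered, one is ambiguous and one has no described control source.

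**2. Why the missing arm matters.** Write the mean outcome as b0 + b1·T + b2·M + b3·T·M, with T the arm and M the above-median indicator. If M is known only when T = 1, the contrast between high and low clusters in the intervention arm gives b2 + b3. Separating b3, the interaction, from b2, the attribute's own association with health, needs M in the control clusters.

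**3. Scaling by uptake.** The plan gives no uptake figure to reproduce. I use its detectable effect of 0.33 SD only as an example intention-to-treat effect. To check that figure, the inputs in Section 9 (Power Calculations) are the error rates ("we assume a Type I error rate of 0.05 and a desired power of 0.8 for the primary outcomes"), 30 clusters per arm of 8 people each, and the clustering ("We assume an intraclass correlation (ICC) of 0.05").

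- Design effect: 1 + 7 × 0.05 = 1.35.
- Standard error in SD units: √(2 × 1.35 / 240) = 0.106.
- Two-sided alpha 0.05: (1.960 + 0.842) × 0.106 = 0.297 (0.302 with t on 58 df).
- Two-sided alpha 0.025: (2.241 + 0.842) × 0.106 = 0.327 (0.334 with t on 58 df).

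So 0.33 matches an alpha of 0.05 split over two primary outcomes, not the stated 0.05. That is a separate matter and does not affect this point.

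Let p1 and p0 be uptake in the intervention and control arms. Assuming no control uptake, the scaled effect is ITT/p1. Using the between-arm difference, it is ITT/(p1 − p0). The relative understatement is 1 − (p1 − p0)/p1 = p0/p1, whatever the size of the ITT effect.

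| p1 (assumed) | p0 (assumed) | 0.33/p1 | 0.33/(p1 − p0) | Understatement |
|---|---|---|---|---|
| 0.70 | 0.05 | 0.47 | 0.51 | 7.1% |
| 0.70 | 0.10 | 0.47 | 0.55 | 14.3% |
| 0.70 | 0.20 | 0.47 | 0.66 | 28.6% |
| 0.80 | 0.05 | 0.41 | 0.44 | 6.3% |
| 0.80 | 0.10 | 0.41 | 0.47 | 12.5% |
| 0.80 | 0.20 | 0.41 | 0.55 | 25.0% |

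The 0.80 rows sit at the plan's own trigger of 20% non-adherence.

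**4. What the ratio means.** When p0 is above zero, ITT/(p1 − p0) is a complier effect rather than an effect on the treated. It also requires assignment to act only through the participation being scaled. Section 9 itself notes that place-based work proceeds without participants' involvement, so it reaches non-adherers too. Any benefit from that work would be credited to financial participation and push the ratio up. The percentages above therefore describe the scaling factor, not the net bias.

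**The case against.** The strongest reply is that these are secondary matters that the plan already qualifies. The mechanism analyses are labelled descriptive and exploratory, and the scaled estimate is contingent. The house list is an operational tool for choosing houses to remediate, not a declared analysis dataset, and its public source could supply control counts. Table 1 lists outcomes, not the questionnaire, and Section 9 mentions participants reporting service use, so the question may already be asked. Controls receive neither the $400 grant nor facilitated engagement, so if participation means the full package, control receipt is zero by design. All of this stands. It limits the point to what the plan fails to state; it does not supply the missing source or measure.

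A reader might infer more than the documents support:

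- *That exposure is recorded only in the intervention arm.* Tax filing, benefit participation, greenspace use and reported abandoned buildings are surveyed in both arms. These are results or perceptions, however, not use of a partner service.
- *That the component interactions in general lack control values.* The moderators are baseline attributes, not delivered exposure, and four of six are covered.
- *That the plan divides by intervention uptake.* It names no estimator.
- *That equivalent greening or façade work occurs in control clusters.* The society's existing lot-care programme shows activity outside the trial, but it is mowing and trash cleanup. Nothing documents the full treatment in control clusters.

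**Conclusion.** The point holds in limited form. One of six moderators, abandoned houses, has no described control-arm source and is printed as a different variable; a second, vacant lots, needs its source stated. Control use of the partner services is expected, but no measure of it is described, so the treatment-on-the-treated analysis cannot allow for it.

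The size of the second gap is conditional. If control uptake were taken as zero, the scaled effect would be understated by 7% to 29% for assumed uptake of 70% in the intervention arm and 5% to 20% in the control arm. The documents give neither rate, and the figures apply only if participation is defined so that controls can have it.

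It would be tempting to conclude that a null primary result becomes uninterpretable. The documents do not support that: the primary comparison is by assignment, and control engagement is part of the comparison condition. The change is still worth making before endline, because service use not asked about then would be hard to recover later.

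**What to change.** 1. In Section 9 (Evaluating Mechanisms), change the moderator to the number of abandoned houses. Compile abandoned-house and vacant-lot counts for all 60 microclusters from the same City and horticultural society lists. Place-based work was due to start in April 2023 and the protocol is dated May 2023, so use archived data from before that start.
2. Add three yes/no endline items in both arms, placed after the primary outcomes, on use of financial counselling, benefits-application help and free tax preparation. Limit recall to the period from enrolment to August 2024, before controls receive the partner list, and report uptake by arm. If the questionnaire already asks this, say so in the plan.
3. In the fourth sensitivity analysis, define one participation measure, scale by the between-arm difference in uptake, and call the result a complier effect. State that place-based work also reaches non-adherers, so the scaling rests on an exclusion assumption and is exploratory.
4. Optionally, describe any society or City work recorded in control clusters.

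The cost is about a minute more survey time and a small desk extraction from lists the study already uses.
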